#### 2.2 Rationale

OA is a slowly degenerative disease that affects the whole joint with impact on the articular cartilage, subchondral bone and the synovial membrane. Identified risks factors for OA include age, sex, obesity, traumatic injuries (post-traumatic OA) and cardiometabolic factors. Dysregulation in glucose, lipid metabolism as well as overall low-grade inflammation are common phenotypes found in OA and metabolic disease, which prompted scientists to suggest that OA was not only a age-related degenerative disease but also a proper component of the metabolic syndrome (metabolic OA) (Kornaat et al., 2009; Courties, et al., 2017).

Glucagon-like peptide-1 (GLP-1) belongs to the incretin family, a group of hormones with glucose-dependent insulin secretion activity. Notably Glucagon-Like Peptide 1(GLP-1) analogues such as liraglutide have been developed and used in humans since 2009 for the treatment of type 2 diabetes mellitus. In recent years, numerous studies have detailed the anti-inflammatory impact of GLP-1 in numerous organs and diseases (Nauck, 2016; Li et al., 2017). Thus, GLP-1 analogues could also prove beneficial for OA treatments.

The non-clinical studies (*in vitro* and *in vivo*) in the literature or conducted by the sponsor with liraglutide provide a mechanistic basis for its primary pharmacological effect for the target indication in OA, whereby liraglutide with its anti-inflammatory, anti-catabolic and anabolic activities acts in concert on the synovial membrane inflammation and the articular cartilage to alleviate OA-related symptoms and structure damages.

GLP-1 binds to the Glucagon-like-peptide-1 receptor (GLP-1 receptor or GLP-1R). In cartilage, GLP-1 receptor is expressed in OA human chondrocytes (Meurot et al., 2022), and the agonist activity of liraglutide on this receptor increases rat chondrocytes viability through increased resistance against cell-stress and apoptosis (Chen et al., 2018). Furthermore, liraglutide dose-dependently decreases the secretion and gene expression of metalloproteinases (MMP-3, MMP-13) and aggrecanases (ADAMTS-4, ADAMTS-5), while increasing the gene expression of Sox9, a transcription factor crucial for chondrocytes differentiation, collagen 2 and aggrecan, thus liraglutide possesses anticatabolic activity and anabolic activities in murine chondrocytes (Meurot et al., 2022). In the destabilization of medial meniscus (DMM) model, a surgically induced OA model in rat, repeated IA injections of liraglutide 60µg for 6 weeks decreases proteoglycan loss resulting in significantly less cartilage degeneration width model of OA (sponsor, see IB), the benefits of liraglutide on cartilage structure is also confirmed in the literature (Chen et al., 2018).

Liraglutide presents strong anti-inflammatory activity and decreases in a dose-dependent manner the secretion of NO, PGE2, IL-6 by murine macrophages and chondrocytes in vitro (with an average IC50 value of 50 nM). In the monoiodoacetate (MIA) rat model of inflammatory OA and pain, a single IA administration of liraglutide dose-dependently decreases pain during von Frey test (mechanically induced pain assessment), with a long-lasting effect of 4 weeks (sponsor). Furthermore, in the MIA-induced OA mouse, single administration of Liraglutide decreases

mechanically induced pain as well as synovial membrane inflammation score (liraglutide  $20 \mu g$ , p = 0.0099, compared to vehicle-treated group) (Meurot et al., 2022).

Additionally, it has been demonstrated that liraglutide GLP-1R agonist does not exhibit cytotoxic effects on chondrocytes, prevents from interleukin-mediated cytotoxicity (Chen et al, 2018) and shows an anti-inflammatory activity through the PKA/CREB pathway activation (Que et al, 2019).

Pharmacokinetic exploration of liraglutide distribution demonstrates that subcutaneous administration does not allow liraglutide passage within synovial fluid of animals while intra-articular administration would provide a synovial exposition. In addition, IA administration of liraglutide leads to systemic level comparable with those observed upon subcutaneous administration. Thus, the intra-articular route of administration is necessary to obtain a local action on OA tissues.

Therefore, and in contrast with the current standard of care in OA, these mechanisms of action allow to prevent structural damages during the evolution of the disease (cartilage protection) and alleviate symptoms with a long-lasting analgesic effect. Thus, IA administration of 4P-004 is expected to act as a disease-modifying OA drug (DMOAD) upon IA administration.

## 2.3 Risk / Benefit Assessment

The safety profile of 4P-004 is well known when administered subcutaneously (for long-term use) but no human data is available regarding the safety profile after IA injection.

As part of its preclinical data package, the sponsor intends to rely on previously published and assessed data of liraglutide containing authorized medicinal products (Victoza®, Saxenda®) to address systemic safety and toxicology of liraglutide. PK studies performed in dogs have shown very reproducibly that there is no more liraglutide after 24h in the articulation after IA injection in the knee-joint (see IB). A GLP extended single dose toxicity study of knee IA administration 4P-004 has been performed in rats. The product was well tolerated, no adverse signs of toxicity were observed up to the higher tested dose of 300 µg, which was determined as the No Observed Adverse Effect Level (NOAEL) dose of the study. Detailed presentation of the GLP-Toxicity study is available in the current IB.

#### Liraglutide adverse events

The most frequently reported adverse reactions during clinical trials were gastrointestinal disorders (repeated subcutaneous administration):

- nausea and diarrhea were very common ( $\geq 1/10$ ),
- vomiting, constipation, abdominal pain, and dyspepsia were common ( $\geq 1/100$  to <1/10).

Headache and nasopharyngitis were also common.

Hypoglycemia was common, and very common when liraglutide is used in combination with a sulfonylurea in patients with type 2 diabetes mellitus (Victoza®).

In clinical trials in overweight or obese patients without type 2 diabetes mellitus treated with Saxenda®, no severe hypoglycemic events (requiring third party assistance) were reported. Symptoms of hypoglycemic events were reported by 1.6 % of patients treated with Saxenda® and 1.1% of

patients treated with placebo; however, these events were not confirmed by blood glucose measurements. The majority of events were mild.

Allergic reactions including urticaria, rash and pruritus have been reported from marketed use of liraglutide. Few cases of anaphylactic reactions with additional symptoms such as hypotension, palpitations, dyspnea, and oedema have been reported with marketed use of Victoza. Few cases (0.05%) of angioedema have been reported during all long-term clinical trials with Victoza.

## Liraglutide overdose

From clinical trials and marketed use, overdoses have been reported of up to 40 times (72 mg) the recommended maintenance dose (Nakanishi et al., 2012). Events reported included severe nausea, vomiting, diarrhea and severe hypoglycemia.

In the event of overdose, appropriate supportive treatment should be initiated according to the participant's clinical signs and symptoms. The participant should be observed for clinical signs of dehydration and blood glucose should be monitored.

Additional details regarding risks for participants in this clinical study may be found in the SmPC/IB and informed consent documents

## Blind review by the Sponsor of ongoing clinical safety data in Cohort 3 (as of 17 July 2023):

After blinded review of clinical safety data in cohort 3 (dose = \_\_\_\_\_, the Sponsor decided that, taking into consideration the benefit/risk for patients and the potential issues of performing a future double-blind study, the Maximum Tolerated Dose may have been reached based on adverse event "nausea" for 5 participants and "vomiting" for 4 of them. Consequently, the Sponsor decided to test an intermediate dose \_\_\_\_\_ in cohort 4 to obtain clinical safety information with this dose. Higher 4P-004 doses than \_\_\_\_\_ will not be tested in this study.

## **3 OBJECTIVES AND ENDPOINTS**

#### 3.1 Objectives

## 3.1.1 Primary objectives

- To characterize safety and tolerability of single IA administration of 4P-004 at escalating doses in participants with knee OA grade 2 to 4 osteoarthritis (OA) on the Kellgren and Lawrence severity index (KL 2-4)
- To determine the maximum tolerated dose (MTD) defined by occurrence of Dose Limiting Toxicities (DLTs) in participants with knee OA KL 2-4.

#### 3.1.2 Secondary objective

• To characterize the plasma PK of liraglutide when administered as single IA doses at escalating dose levels in participants with knee OA KL 2-4.

## 3.1.3 Exploratory objectives

• Collection of biological fluids (blood, urine).

## 3.2 Endpoints

#### 3.2.1 Primary endpoints

- Number of Adverse events (AEs), serious AEs (SAEs) (Common Terminology Criteria Adverse Events [CTC-AE]) from ICF signature to D29, including target knee pain and tenderness, erythema, swelling, local pain at injection site.
- Vital signs from D-7 to D8, ECG from D-7 to D1: Mean change, number of Potentially Clinically Significant Abnormality (PCSA), Percentage of participants with PCSA
- Laboratory changes (Red Blood Cells (RBC), White Blood Cells (WBC), Hemoglobin (Hb), platelets, alanine transaminase (ALT), aspartate transaminase (AST), glycemia, amylasemia, creatinin clearance) from D-7 to D8: Mean changes number of PCSA, Percentage of participants with PCSA.

## 3.2.2 Secondary endpoint

• Plasma concentration of liraglutide following a single IA injection. PK samples: D1 preinjection (T0-4h) and 2, 4, 8, 12, 16 and 24 hours post injection.

Plasma concentrations will be performed by

## 3.2.3 Exploratory endpoints

• Serum and urine OA-related biomarkers (exploratory proteomic research of 4P-004 efficacy-related biomarkers) at D1 (T0-4h, T0+8h), D2 (T0+24h) and D8.

Human blood serum and urine samples will be collected and shipped to AO Research Institute Davos for liquid biomarker identification.

#### 4 STUDY DESIGN AND DESCRIPTION

#### 4.1 Overall design

Phase I study for IA injection, double-blind, placebo-controlled, randomized, multicenter, single ascending dose is designed to assess the safety, tolerability and pharmacokinetic of 4P-004 in participants with target knee OA KL 2-4.

Participants will be enrolled in 4 cohorts; in each cohort participants will receive either 4P-004 or placebo (6:2). 4P-004 dose will increase with cohort 1 to 4.

For the highest dose cohort a sentinel dosing will be implemented (see section 4.2).

## Recruitment of participants

Participants will be recruited via investigators' patient registry or via advertising. More information is provided in Patient Recruitment Procedure.

A Screening visit at D-7 (D-14 to D-4) will be performed at study site and if the participant still agrees to participate in the study after the investigator has answered all his/her questions, the participant will sign the informed consent form. This visit should take place around 7 days before the randomization day (D-14 to D-4). During this visit, the eligibility of the participant will be evaluated.

The Randomization visit (Day 1 to Day 2) will be performed at study site and the participant will be randomized in the study after review of inclusion & exclusion criteria. The participant will be hospitalized for 24 hours. The IMP IA injection will be performed by the investigator after a veinous infusion line has been set up (see Investigator & Pharmacy manuals and sections 1.2 and 6.2.2). Participant will be monitored during the 24-hour hospitalization and will be discharge on D2.

The Follow-up visit at D4 (±1 day) will be a virtual visit by phone call unless abnormal, clinically significant findings are observed upon discharge or at the investigator's discretion (participants should then be brought back to the clinic for re-evaluation).

The Follow-up visit at D8 ( $\pm 2$  days) will be a face-to-face visit. Participant will be asked to fill in a diary and a NRS questionnaire up to Day 29 to record any AE (in particular pain in the target knee) and analgesic medication taken.

The End of Study (EoS) visit at D29 (±2 days) will be a virtual visit by phone call unless abnormal, clinically significant findings are observed upon discharge or at the investigator's discretion (participants should then be brought back to the clinic for re-evaluation). Participant will be asked to send back to the Investigator the diary and the NRS questionnaire

An independent Data and Safety Monitoring Board (DSMB) will be set up for this study (see DSMB Charter) and will review safety data during the study. The DSMB will be composed of 2 physicians specialized, one in rheumatology and one in diabetology.

Members will review the safety data in sessions on a regular basis during the study, and at any time if any SAE at least possibly related to liraglutide or safety issue occurs (see section 11.1.5 and DSMB Charter).

#### 4.2 Scientific rationale for study design

This phase 1 study is randomized, double-blinded, and placebo-controlled in order to avoid subjective bias in the assessment of the safety and tolerability of 4P-004.

To mitigate risks associated with 4P-004, first IA injection in human, hypoglycemic properties and other potential risks based on preclinical and clinical data:

- Participants are enrolled in 4 cohorts with IMP dose increasing from cohort 1 to 3;
- Study-specific eligibility criteria have been added to the standard criteria to ensure that participants at increased risk of hypoglycemia are excluded (see section 5.2);
- A DSMB is set up;
- Two sentinel participants are included for the highest tested dose evaluation (including lab safety but not PK data) of these sentinel participants will be reviewed by the DSMB before randomization of the next participant;

#### 4.3 Justification for route of administration

Pharmacokinetic studies have been performed with liraglutide in dogs (Study report 4P004-027-PK see IB). This study demonstrates that:

- subcutaneous administration (authorized route of administration) of liraglutide does not allow diffusion into the synovial fluid,
- upon IA administration, liraglutide exhibit similar systemic blood exposure as upon subcutaneous administration.

Thus, to expose the diseased tissue, local IA administration is necessary.

4.4 Justification for dose
As part of this phase I trial, four different dose levels of 4P-004 will be investigated:  These dose levels have been selected considering the results of pharmacological data (efficacy) and toxicological data (safety) (see IB for detailed justification on dose selection).
Dose 1 (starting dose; ):
is the human starting dose considered for the clinical trial. is the Minimum anticipated biological level dose (MABEL). It is assumed that both safety and potential clinical benefit for the patient are ensured with this first dose of which is in line with EMEA/CHMP/SWP/28367/07 Rev. 1 considerations.
Dose 2
in human is around the effective dose leading to an optimal analgesia effect of 4P-004 in induced osteoarthritis rat model following human equivalent dose (HED) conversion.
Dose 3
Sentinel participants will be included for this dose-cohort during the clinical study.

## 4.5 End of study definition

The overall study ends when the last participant completes the last study-related contact, withdraws consent, or is lost to follow-up (i.e., the participant is unable to be contacted by the investigator).

## 4.6 Early study termination

The study will be completed as planned unless one or more of the following criteria are satisfied that require temporary suspension or early termination of the study.

The clinical study may be terminated early if new information or other evaluation regarding the safety or efficacy of the study drug that indicates a significant change in the known risk/benefit profile for the drug, such that the risk is no longer acceptable for participants participating in the study.

## 4.6.1 Clinical criteria for early study termination

It is agreed that for reasonable cause, either the investigator or the Sponsor may terminate this study, provided a written notice is submitted at a reasonable time in advance of intended termination; if by the investigator notice is to be submitted to the sponsor and if by the Sponsor, notice will be provided to each investigator.

## Stopping rules

The study will be immediately suspended, and no additional IMP administered pending review and discussion of all appropriate study data by the DSMB if 1 or more participants develop any of the following adverse events deemed to be possibly, probably, or definitely related to the IMP by the Investigator and/or Medical Monitor, based upon close temporal relationship or other factors:

- Severe local reaction within 7 days after injection
- Clinical manifestations of hypoglycemia
- Severe gastro-intestinal adverse event
- Potentially clinically significant ECG abnormalities.
- Any serious adverse event considered reasonably related to the IMP (SAR) by the Principal Investigator.

The study will not be restarted until all parties have agreed to the course of action to be taken and the EC has been notified.

Dose limiting toxicity (DLT) describes side effects of a drug that are serious enough to prevent an increase in dose or level of that treatment.

When more than 1 DLT occurs in a dosing cohort, dose escalation must be stopped and this dose level will be identified as the non-tolerated dose.

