## **Data and Safety Monitoring Board (DSMB)**

The DSMB will be composed of 2 independent physicians specialized, one in rheumatology and one in diabetology.

After each dose level completion (and at any time if needed), a DSMB evaluation based on a safety data analysis is intended by the sponsor before moving forward to the next higher dose level (or to randomize the next participant).

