#### DLT is based on:

- Expert's opinion
- Any related SAE

In this study, with liraglutide, DLT will be established if any of the following occurs:

- Anaphylaxis (angioedema, hypotension, shock, bronchospasm, hypoxia, or respiratory distress),
- Hypoglycemia (blood glucose level  $\leq 2.5$  mmol/L) within 2 days after injection,
- Amylasemia  $\geq$  3ULN within 7 days after injection,
- Serious gastro-intestinal adverse event within 7 days after injection.

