## 8.2.6 Adverse event of special interest (AESI)

An AESI is an AE (serious or nonserious) of scientific and medical concern specific to the Sponsor's product or program, for which ongoing monitoring and immediate notification by the Investigator to the Sponsor or designee is required.

All reported AESIs will be reviewed by an independent DSMB.

For AESIs, the Sponsor is to be informed immediately (i.e., within 24 hours), as per SAE notification guidelines described in section 11.3, even if a seriousness criterion is not met, using the corresponding pages of the case report form (to be sent) or screens in the eCRF:

- Pregnancy of a female participant entered in a study as well as pregnancy occurring in a female partner of a male participant entered in a study with IMP. It will be qualified as an SAE only if it fulfills one of the seriousness criteria (see section 11.3). Follow-up of the pregnancy in a female participant or in a female partner of a male participant is mandatory until the outcome has been determined (see section 11.4).
- Symptomatic overdose (serious or non-serious) with IMP. Any adverse event(s) associated with ("results from") an overdose of IMP will be reported as a serious adverse event, even if no other seriousness criteria are met.

Other project specific AESI:

- Anaphylaxis,
- Severe IMP injection site reactions (severe tenderness, erythema, swelling...),
- Hypoglycemia,
- Severe Gastro-intestinal disorder.

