#### 11.1.8 Study and site start and closure

The study start date is the date on which the clinical study will be open for recruitment of participants. The first act of recruitment is the first site open and will be the study start date.

The Sponsor or designee reserves the right to close the study site or terminate the study at any time for any reason at the sole discretion of the Sponsor. Study sites will be closed upon study completion. A study site is considered closed when all required documents and study supplies have been collected and a study-site closure visit has been performed.

• Note: in case of investigational site closure or complete regional or national lock-down due to a local epidemic or international pandemic, the study may be suspended regionally or nationally at the affected sites. Every effort will be made to continue the follow-up of already recruited participants as close to the SoE as possible.

The Investigator may initiate study-site closure at any time, provided there is reasonable cause and sufficient notice is given in advance of the intended termination reasons for study termination by the Sponsor, as well as reasons for the early closure of a study site by the Sponsor or Investigator may include but are not limited to:

- For study termination:
  - o Information on the product leading to doubt regarding the benefit/risk ratio,
  - o Discontinuation of further study intervention development.
- For site termination:

- Failure of the Investigator to comply with the protocol, the requirements of the IEC or local health authorities, the Sponsor's procedures, or GCP guidelines,
- o Inadequate or no recruitment (evaluated after a reasonable amount of time) of participants by the Investigator,
- o Total number of participants included earlier than expected.

If the study is prematurely terminated or suspended, the Sponsor shall promptly inform the Investigators, the IECs, the regulatory authorities, and any Contract Research Organization(s) used in the study of the reason for termination or suspension, as specified by the applicable regulatory requirements. The Investigator shall promptly inform the participant and should assure appropriate participant therapy and/or follow-up.

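### The SAE line of the mandatory suspension rule names a different assessor and an undefined standard from its lead-in, so an SAE called related only by the Medical Monitor may not stop dosing

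*Protocol*

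**What the plan says.** The stopping rules in Protocol 4.6.1 require immediate suspension, with no further IMP until the DSMB has reviewed the data, once one or more participants have a listed event. A lead-in sets the causality condition for the whole list: the event must be "deemed to be possibly, probably, or definitely related to the IMP by the Investigator and/or Medical Monitor".

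Five kinds of event follow. The first four (severe local reaction in the first week, symptomatic hypoglycemia, severe gastrointestinal event, significant ECG abnormality) have no causality wording of their own. The fifth does: "Any serious adverse event considered reasonably related to the IMP (SAR) by the Principal Investigator".

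Restart after a suspension needs the agreement of all parties and notification of the ethics committee.

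The same section has a separate escalation rule: "When more than 1 DLT occurs in a dosing cohort, dose escalation must be stopped". Anaphylaxis is one of the named DLTs.

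**The concern.** The fifth bullet changes two things at once. The assessor becomes the Principal Investigator alone, and the standard becomes *reasonably related*. A site can read this in two ways:

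- the extra words are redundant and the lead-in governs; or
- they are an added condition that the Principal Investigator must find met.

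The two readings part when the Medical Monitor considers an SAE possibly related, the Principal Investigator does not, and the event falls under none of the first four bullets. Anaphylaxis is the natural example. It is both a DLT and an adverse event of special interest, yet it is not among the first four bullets, so unless it also meets one of them it reaches the suspension rule only through the fifth.

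If the fifth bullet is not met, the study loses the hold on dosing, the all-party restart condition and the ethics committee notification. This is a first intra-articular use in humans at three sites, so several people have to apply the rule in the same way.

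**Working it through.** The plan gives no figure to reproduce. The check compares the texts and then counts logical cases.

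**1. The two tests side by side (Protocol 4.6.1)**

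| | Lead-in | Fifth bullet |
|---|---|---|
| Who judges | Investigator, Medical Monitor, or both | Principal Investigator |
| Standard | possible, probable or definite | *reasonably related* |
| Applies to | every listed event | SAEs |

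**2. Is the second standard defined?** The scale in Protocol 11.3.4 has Definitely, Probable and Possible (reported as related) and Unlikely and Unrelated (reported as not related). *Reasonably related* is not a level. Its only other use, for post-study pregnancy SAEs in Protocol 11.4.3, is also undefined. The abbreviation SAR is missing from both abbreviation lists. This does not show that the standard is higher than *possible*, only that it is not defined. The SAP does not address the rule.

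**3. Logic.** Let P mean that the Principal Investigator calls the SAE related, M that the Medical Monitor does, and *inside* that the SAE also meets one of the first four bullets.

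- Lead-in governs: suspend if (P or M).
- Literal reading: suspend if [inside and (P or M)] or [P and (P or M)]. The last bracket reduces to P.

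| SAE type | Who calls it related | Lead-in governs | Literal reading |
|---|---|---|---|
| Inside | both | suspend | suspend |
| Inside | Principal Investigator only | suspend | suspend |
| Inside | Medical Monitor only | suspend | suspend |
| Inside | neither | no | no |
| Outside | both | suspend | suspend |
| Outside | Principal Investigator only | suspend | suspend |
| Outside | Medical Monitor only | **suspend** | **no** |
| Outside | neither | no | no |

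Totals: 3 + 3 = 6 of 8 if the lead-in governs, and 3 + 2 = 5 of 8 on the literal reading. The difference is 6 − 5 = 1 case. These are logical cases, not probabilities.

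**4. Does other text hold dosing in that one case?**

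- Synopsis, DSMB: evaluation after each dose level, and at other times if needed, "is intended by the sponsor before moving forward to the next higher dose level (or to randomize the next participant". This states an intention, not a hold.
- Protocol 4.1: the DSMB reviews data "at any time if any SAE at least possibly related to liraglutide or safety issue occurs". No assessor is named and no pause is attached.
- Protocol 8.2.6: "All reported AESIs will be reviewed by an independent DSMB". Again, no pause is attached.
- DLT rule: one anaphylaxis is one DLT, and escalation stops only at more than one in a cohort. Stopping escalation does not stop dosing at the current level.
- Protocol 11.1.8: the sponsor may "terminate the study at any time for any reason at the sole discretion of the Sponsor". This is discretionary.
- Sentinel review (Protocol 4.2 and 4.4) is tied to the highest dose. Section 2.3 makes cohort 4 an intermediate dose, so this review does not expressly cover it.

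**5. Exposure.** There are 4 cohorts of 8, 32 in all, randomized 6:2. Under this version dosing still to come is mainly cohort 4: 8/32 = 25% of planned participants, 6 of them on active drug. Any cohort 3 participant not yet dosed adds to this; that number is not stated.

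**The case against.** The strongest reply is that the lead-in is the better governing text. It covers the whole list and deliberately gives the Medical Monitor independent standing, and nothing suggests that SAEs were meant to have weaker protection than ECG changes. The fifth bullet may be no more than a loose gloss on *serious adverse reaction*, a term that Protocol 11.3.3 uses. *Reasonably related* also fits easily with the broad Related category in 11.3.4, which includes events where a role for the drug cannot be ruled out.

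The example is also uncommon: a Principal Investigator would have to call anaphylaxis after an observed injection unrelated, although allergic reactions to liraglutide are acknowledged in Protocol 2.3. The event would still reach the DSMB through 4.1 and 8.2.6, and the DSMB charter, which is not available here, may provide for a hold. The case count carries no weights.

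Much of this stands. The sponsor probably meant the lead-in to govern, the DSMB would probably be consulted, and the disputed case is likely to be infrequent. These points limit the practical harm. They do not remove the conflict, because the fifth bullet's extra words invite a site to apply them. None of the visible safeguards imposes an automatic hold, and a charter provision would not make the protocol's own rule consistent.

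**Conclusion.** The concern holds. The suspension rule contains two relatedness tests for SAEs, and no text chooses between them. On the literal reading, an SAE outside the first four bullets that only the Medical Monitor calls related does not suspend dosing.

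The effect is confined to that one case of eight. The rule acts on a single participant, so one such event would be enough to matter. Its frequency cannot be estimated from the documents.

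The count assumes that the Principal Investigator is an Investigator for the purposes of the lead-in, and that a Principal Investigator who finds an SAE reasonably related also rates it at least possible.

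Severity is minor: no endpoint, analysis set or estimate is affected. Confidence in the inconsistency is high.

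**What to change.** Shorten the fifth bullet to *Any serious adverse event*. The lead-in then supplies the assessor (either party) and the threshold (possible or stronger) for all five bullets. Protocol 4.1 needs no change, since its trigger for DSMB review already uses the same threshold.

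The cost is one line of protocol wording. The only operational downside is a possible extra temporary pause for DSMB review when the Medical Monitor alone considers an SAE related.
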